### 3. Relations to other variables:

We will analyze variation in performance scores (TBS and mGEARS) between experienced robotic cardiac surgeons and robotic novices during their base-line performance. We will use TBS score for the assessment of novice performance during the subsequent training rounds.

### 4. Internal structure:

To examine the reliability of the final simulator task, the internal consistency and test/retest reliability will be assessed. The internal consistency of TBS and mGEARS scores will be used for the assessment of trainee performance for the base-line task. The test/retest reliability will be calculated by comparing the trainees' TBS and mGEARS performance in the last 2 training sessions.

## 5. Consequences:

To investigate the consequence of testing we will define a pass/fail level to be used for mastery learning. The pass/fail level will be determined using the “contrasting groups method” for the mean TBS and mGEARS score for the last two attempts in the experienced group.

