## **Materials and methods**

We aim to assess the validity evidence for the wet lab robotic cardiac surgery simulation model using the contemporary framework for validity proposed by Messick, which includes five sources of validity evidence: content evidence, response process, relations to other variables, internal structure, and consequences.

We will test the validity evidence for the three wet lab tasks used in robotic cardiac surgery using three groups of participants: experienced robotic cardiac surgeons (5), robotic cardiac surgery novices (8) and robotic non-cardiac surgery novices (8).

Wet lab simulator: tasks will be performed in porcine models with the da Vinci Xi Surgical System (Intuitive Surgical, California, USA).

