### 2. Response process:

All participants will receive a short oral introduction to the da Vinci Xi Surgical System and will be shown videos of robotically assisted cardiac procedures highlighting basic operative techniques and relevant anatomy. They will then complete the three previously selected tasks to familiarize themselves with the wet lab simulator. Finally, they will complete all 3 tasks again and this will be used to assess their base-line performance.

Next, five experienced robotic cardiac surgeons from different international sites will perform each task 4 times more. Subjects in the cardiac and non-cardiac groups will perform the tasks until mastery is achieved based on the performance of the expert robotic surgeons. To ensure

the successful completion of the task, each participant will be required to pass each exercise 2 consecutive times with the only one failure between the attempts allowed.

The mastery learning level for the tasks will be calculated from the mean time-based score (TBS) of the experienced surgeons 2 last attempts for each task.

Time-based scoring equation will be calculated as follows (adapted from Valdis et al):

$$\text{Score} = \text{Max time} - \text{Completion time} - \text{Errors}$$

-Max time is the total time that an individual will be allowed to complete the task during the base-line performance.

-Completion time is either;

- 1) The mean time for completion of each expert's last 2 attempts which will be used to calculate the mastery learning level based on the formula above
- 2) The time taken by each study participant to complete the task

- Errors will be divided in minor and major ones. A minor error will result in adding a 10 second penalty time to the TBS equation. A major error will result in a score of zero, regardless of time to completion.

Minor errors:

- 1) moving robotic arms out of view
- 2) robotic arm collision
- 3) drop of the needle

Major errors:

- 1) avulsion of ITA or suturing model
- 2) tearing/ fraying the suture
- 3) gross tissue damage (specifically with the cautery)

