### Statistical plan and data analysis

Within the current literature exists the only study assessing robotic cardiac surgery simulation training with sample size of 10 participants in the wet lab group. The reports on growth models and learning curve dataset recommend least 3 repeated observations per individual. We plan to recruit 16 participants in the novice and 5 robotic cardiac surgeons from different international sites in the experienced group. We plan to include equal numbers of cardiac (8) and non-cardiac trainees (8). Additionally, two surgeons with experience in robotic cardiac surgery from two different sites will be recruited to rate all the training sessions.

Based on the previous study we hypothesize that the subjects in the novice group will be able to achieve the mastery learning within 5 trainings sessions and thus fulfil the requirement of at least 3 repeated observations.

STATA will be used for statistical analysis. The Kruskal-Wallis test will be used to examine a difference between the novice and the expert group at base-line. We will use the Mann-Whitney U test to compare continuous variables. A two-sided significance level of 0.05 will be used. The internal consistency will be evaluated by Cronbach's alpha, and the test/retest reliability of the last two training sessions using intra-class correlation coefficient.

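### The consequences evidence defines a pass/fail level but never checks how that level classifies known experts and base-line novices

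*Combined protocol and SAP*

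**What the plan says.** The primary objective is validity evidence for the wet lab assessment. Materials and methods organises it under five sources, of which consequences is the fifth. That section opens with "To investigate the consequence of testing we will define a pass/fail level to be used for mastery learning". Its second sentence, which takes its data from the experts only, begins as follows: "The pass/fail level will be determined using the “contrasting groups method” for the mean TBS and mGEARS score for the last two attempts in the". Nothing else is said under that source.

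Section 2 (Response process) sets the level used in training in a different way, separately by task, in a sentence that begins: "The mastery learning level for the tasks will be calculated from the mean time-based score (TBS) of the experienced surgeons 2 last attempts for each". It then says "Subjects in the cardiac and non-cardiac groups will perform the tasks until mastery is achieved based on the performance of the expert robotic surgeons", and "each participant will be required to pass each exercise 2 consecutive times with the only one failure between the attempts allowed". No maximum number of attempts is stated. Section 3 (Relations to other variables) adds "We will use TBS score for the assessment of novice performance during the subsequent training rounds", so the mGEARS pass/fail level is not the one novices train to.

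The Statistical plan lists a Kruskal-Wallis test of novices against experts at base-line, Mann-Whitney tests, Cronbach's alpha and an intra-class correlation. It also says "we hypothesize that the subjects in the novice group will be able to achieve the mastery learning within 5 trainings sessions", which it uses to support having at least three repeated observations per person. There are 16 novices (8 cardiac, 8 non-cardiac) and 5 experts.

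**The concern.** Defining a level is a calculation, not a test of the level. What matters about a pass/fail standard is whom it wrongly passes and whom it wrongly fails, and the plan asks for neither. The only pass results it generates come from novices who repeat the tasks until they pass, so those results carry almost no information about whether the level sits in the right place.

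The Study rationale wants a level that secures competency before a surgeon operates on patients. As written, the study could report its consequences evidence as complete even if a large share of base-line novices already cleared the level, or if experts fell below it. The scores that would show this are collected but not used for the purpose.

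**Working it through.** **1. Does any planned analysis use the level?** Kruskal-Wallis and Mann-Whitney compare score distributions. Cronbach's alpha and the intra-class correlation describe reliability. None takes a cut-off as input. Training time to mastery (a secondary outcome) depends on the training level, but it has no threshold and is not linked to the consequences source. The documents give no figure for this source, so there is nothing to reproduce.

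**2. What does eventual mastery show?** Assume a constant per-attempt pass chance *p* and independent attempts. The mean number of attempts to two consecutive passes is (1 + p)/p²:
- p = 0.3: 1.3/0.09 = 14.4
- p = 0.5: 1.5/0.25 = 6.0
- p = 0.7: 1.7/0.49 = 3.5

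This is finite for every p above zero, so a novice who never improves still passes eventually. Allowing one failure between the passes only shortens the wait. These values of p are assumed and illustrate the training rule; they do not measure the contrasting-groups level.

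**3. Does a group difference settle classification?** Assume normal scores with equal SD, groups separated by *d* SD, and a cut midway. The false-pass and false-fail rates are then both Φ(−d/2): 50% at d = 0, 31% at d = 1, 16% at d = 2 and 7% at d = 3. The documents give no separation, so this is a range and not a forecast. It shows that groups can truly differ while the cut still misclassifies many people.

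**4. How precise would the missing proportions be?** With zero events among *n*, the exact two-sided 95% upper limit is 1 − 0.025^(1/n).
- Novices: 0/16 gives 1 − 0.025^(1/16) = 20.6%. For comparison, the exact interval for 8/16 is 24.7% to 75.3%, which does not overlap.
- Experts: 0/5 gives 1 − 0.025^(1/5) = 52.2%. For 2/5 the interval is about 5% to 85%.

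**5. Are the natural comparison points equivalent?** Under Response process, everyone does one familiarisation round and then the base-line round. Experts then do four more. Novice base-line is therefore round 2, and the experts' last two attempts are rounds 5 and 6 (1 + 1 + 4 = 6). Comparing only these would mix practice with skill. Expert base-line is also round 2, so a like-for-like comparison is available.

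**6. Which level is to be checked?** Response process uses the expert mean; Consequences names contrasting groups. If expert scores are roughly symmetric, about half of expert attempts fall below their own mean, so the expert false-fail rate under an expert-mean level is near 50% by construction. A major error sets TBS to zero, so symmetry is not assured. The two descriptions need reconciling before any error rate can be interpreted.

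**The case against.** The strongest reply is that consequences is one source among five and that another already guards against a worthless score. This stands. Sections 3 and the Statistical plan compare experts with novices at base-line. In 10,000 simulated studies with 5 experts and 16 novices drawn from the same normal distribution, the Kruskal-Wallis test was significant in 5.4%, so such a score would usually be exposed there. A reader might infer that the whole validity argument cannot fail, or that a score unrelated to skill would go unnoticed. The documents do not support that.

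Second, a genuine contrasting-groups analysis uses two score distributions and could itself come out badly: there may be no usable crossing point, or the error rates may be near 50%. That is true of the method. However, the section names only experienced-group scores as data and commits to reporting no error rates, so the possibility is not realised in the plan as written.

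Third, mastery within five sessions and training time could both disappoint. They could, but the first serves the count of repeated observations and neither is tied to the level's validity. Nor does the plan say that universal mastery will be offered as evidence; a reader might infer that, but it is not in the text.

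Finally, error proportions alone do not create a possible negative result unless an unacceptable value is stated beforehand. This is right, and the fix includes one.

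**Conclusion.** The concern holds for the consequences source only. The plan defines a pass/fail level and never examines how it classifies people of known status, and passing under uncapped training is not evidence for it. This rests on the text, not on a distributional assumption.

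The size of any misclassification is unknown, because the documents give no score distribution or separation. What can be stated is the precision available: useful for novices (0/16 excludes a false-pass rate above 20.6%) and poor for experts (even 0/5 cannot exclude a false-fail rate of one half). The change is worth making before the analysis; the study can run without it, but this part of its claim would be untested.

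**What to change.** First reconcile the level under Response process with the level under Consequences, stating which groups' scores enter the contrasting-groups calculation. Keep the sentence that defines the level. Then add the following to the Consequences section and the Statistical plan:

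- For each task, and for TBS and mGEARS separately, apply the contrasting-groups level to the 16 novices' base-line attempts and report the false-pass proportion.
- Apply it to the experts at base-line and at their last two attempts and report the false-fail proportion. Count by surgeon, with a stated rule for combining the two attempts.
- Recompute the level without the person being judged, and give each proportion an exact 95% confidence interval.
- State in advance what proportion would count against the level.
- State that reaching mastery in open-ended training is not consequences evidence.

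The cost is a few sentences and one table of 3 tasks × 2 scores × 3 proportions = 18 entries, from scores already planned; no extra participants, attempts or raters are needed. The downsides are that the expert estimates will be very imprecise with five surgeons, and that the result may be less favourable than a bare statement that a level was set.

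### The pass/fail level is assigned to the contrasting groups method but only expert scores are named, so as written it has no crossing point and reduces to the expert mean

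*Combined protocol and SAP*

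**What the plan says.** Under Materials and methods, section 5 (Consequences), the plan states that "we will define a pass/fail level to be used for mastery learning", and that this level will be "determined using the “contrasting groups method” for the mean TBS and mGEARS score for the last two attempts in the experienced group". The section contains nothing further: no novice data set, no intersection rule and no error rates.

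Section 2 (Response process) sets a mastery level for TBS, "calculated from the mean time-based score (TBS) of the experienced surgeons 2 last attempts for each task". Novices "will perform the tasks until mastery is achieved based on the performance of the expert robotic surgeons", and must "pass each exercise 2 consecutive times with the only one failure between the attempts allowed".

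Section 3 (Relations to other variables) compares TBS and mGEARS "between experienced robotic cardiac surgeons and robotic novices during their base-line performance". It does so to show that the scores separate the groups, not to set a standard. The statistical plan names tests and reliability coefficients but does not mention the pass/fail level.

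**The concern.** The contrasting groups method needs two score distributions, one from people taken to be competent and one from people taken not to be. The place where they cross is the cut-off, and the two tails beyond it are the false-fail and false-pass rates. Section 5 names the method but supplies one group and one summary, the mean.

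This matters because the five validity sources listed at the start of Materials and methods carry the primary objective, and section 5 is the whole of the consequences source. The study rationale also gives the lack of a suitable pass/fail level as a reason for doing the study. A level without misclassification rates does not show what follows from using the test.

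There is a knock-on effect. Section 5 says its level serves mastery learning, and section 2 already has a mastery level. Training time to mastery is a secondary outcome, so it must be clear which level stops the clock.

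**Working it through.** The documents state no cut-off or expert fail rate, so there is no figure of the plan's own to reproduce. Score means, SDs, shapes and error rates are not given; every value below for these is an assumption.

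**Inputs from the plan**
- Experts: "five experienced robotic cardiac surgeons from different international sites will perform each task 4 times more", after one familiarisation and one base-line attempt. Their last two are therefore attempts 5 and 6, giving 5 × 2 = 10 attempts per task.
- Novices: 16, each with base-line TBS and mGEARS at attempt 2.
- Zero scores: "A major error will result in a score of zero, regardless of time to completion".

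**Step 1. What the named inputs can give.** The cut-off c solves f_expert(c) = f_novice(c). Without f_novice there is no equation to solve. The remaining quantity is the expert mean over the last two attempts. For TBS that is the section 2 mastery level; for mGEARS section 2 has no counterpart.

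**Step 2. Share of expert attempts below the expert mean**
- Symmetric scores: Φ(0) = 50%.
- Lognormal completion times with log-SD s, share = 1 − Φ(s/2): 46%, 42% and 38% for s = 0.2, 0.4 and 0.6.
- Zeros (probability q) counted in the mean, non-zero scores normal with mean/SD = k, share = q + (1 − q)Φ(−qk). For k from 3 to 8: 38–47% at q = 5%, 29–44% at 10%, 24–42% at 20%.
- Zeros kept out of the mean but counted as fails, share = q + (1 − q) × 0.5: 52.5%, 55% and 60% at q = 5%, 10% and 20%.

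Both treatments of zeros are open, because section 2 describes the level once as a mean of scores and once through a mean of completion times.

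**Step 3. What a two-group cut-off would give.** Take experts as N(0, 1) and novices as N(−d, r²), in expert SDs.

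| d | r | cut-off | experts failing | novices passing |
|---|---|---|---|---|
| 1 | 1 | −0.50 | 30.9% | 30.9% |
| 2 | 1 | −1.00 | 15.9% | 15.9% |
| 3 | 1 | −1.50 | 6.7% | 6.7% |
| 4 | 1 | −2.00 | 2.3% | 2.3% |
| 2 | 2 | −1.24 | 10.8% | 35.2% |
| 3 | 2 | −1.42 | 7.8% | 21.5% |

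With r = 1 the cut-off is −d/2. For d = 1 and r = 2 no crossing lies between the two means, so the rule must also say what happens then.

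**Step 4. Which novice scores could be added.** Novice base-line is attempt 2, against expert attempts 5 and 6, so exposure differs. Novices' last attempts were reached by meeting the expert-based target, so they do not represent a non-competent group. Base-line is the usable set.

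**Step 5. Precision on the expert side.** In SD units and with within-expert correlation ρ, the standard error of the expert mean from two attempts each is √((ρ + (1 − ρ)/2)/5) = 0.36 for ρ = 0.3 and 0.41 for ρ = 0.7. From one base-line attempt each it is √(1/5) = 0.45.

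**The case against.** The strongest reply is that section 5 is incomplete rather than unworkable. The method's name implies a second group, the design has one, and its base-line scores are collected on both instruments. On that view section 5 only says which expert attempts enter. This stands as far as the design goes. A reader might infer that contrasting groups cannot be used in this study; the documents do not support that. But no section says which novice scores would enter or how, and an analyst would have to choose after seeing data.

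Second, section 5 never says that its level is the expert mean, and an expert mean can be a deliberate, demanding training target. Experts set the section 2 level; they are not examined against it. This also stands. The share of experts below the mean counts against calling that mean a contrasting-groups standard, not against training towards it.

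Third, the size is fragile. It is tempting to say that half of experts would fail, or that only a quarter would pass twice running. The first is exact only for symmetric scores. The second (0.5² = 25%) assumes independent attempts and ignores the one failure that section 2 allows. Within three attempts the chance is 0.25 + 0.125 = 37.5%, or 50% if pass-fail-pass counts. Likewise, the 6.7% in step 3 depends on an assumed 3-SD separation.

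Fourth, equal exposure is not obligatory. Experts' later attempts, after adapting to the porcine model, are a defensible picture of competence, and using base-line only would cut expert data from 10 to 5 attempts per task. This is right, and the choice should be stated and tested rather than imposed.

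**Conclusion.** The point holds as a fault in the stated rule. Section 5 names a two-group method, supplies one group, and so gives no intersection and no error rates. Its inputs yield the expert mean, which for TBS duplicates the section 2 mastery level. About half of expert attempts lie below that mean if scores are roughly symmetric, and about 24% to 60% under the skew and zero-score assumptions tried. How far a true contrasting-groups cut-off would differ cannot be known from the documents; it depends on the expert–novice separation and the two spreads.

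A reader might also infer that the primary outcome is compromised. It is not: the base-line comparison of TBS between experts and novices does not use the pass/fail level. What is affected is the consequences evidence and, if sections 2 and 5 are not aligned, the meaning of time to mastery.

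**What to change.** Rewrite section 5 so that, for each task and separately for TBS and mGEARS, the pass/fail level is the intersection of the expert score distribution with the novice base-line distribution. The text should:
- state which expert attempts enter, either base-line (equal exposure, 5 attempts per task) or the last two (10 attempts per task), and run the other as a sensitivity analysis;
- state how zero scores from major errors enter the distributions, and what is done if no crossing lies between the group means;
- report the share of experts failing and of novices passing, with uncertainty intervals that respect repeated attempts by the same expert.

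Then reconcile sections 2 and 5: is there one level or two, what is each called, and which one ends novice training? The expert mean can remain as a training target under its own name.

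The cost is protocol wording and a small analysis of scores already planned; no new data are needed. With 5 experts the cut-off will be imprecise, and it may lie below the expert mean. A level built on novice base-line scores also cannot be fixed until those scores are in, which matters if it is the level chosen to end training.

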### Selection of participants:

#### *Inclusion criteria*

- Experienced robotic cardiac surgeons: robotic surgeons with total volume > 50 robotic cardiac operations and at least 20 robotic cases annually.
- Cardiac surgery novices: on-going or completed cardio-thoracic residency.
- Non-cardiac surgery novices: on-going or completed surgical specialty residency (gynecology, urology, general surgery, ENT surgery).

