Learning curves are increasingly used in the assessment of competency and training program design. Methods currently used to analyze learning curves in surgery are mainly descriptive and need to be rigorous with quantifiable parameters to allow future surgeons to benefit from established performance standards. Data on learning curves in robotic cardiac procedures in a real-world setting exists, but little is known about learning curves in a wet lab simulation setting. Learning curves can support a competence-based approach to assessment for learning. It has been claimed that surgeon expertise in performing both routine and high-risk cardiac procedures before proceeding to robotic-assisted surgery is essential. However, it is possible that as robotic simulators evolve, the non-robotic experience gap may be substantially reduced. By contrast, according to the expertise reversal effect, an instructional design that is beneficial to a novice learner may be detrimental to a more experienced learner and vice versa. The skills acquisition rate of robotic novices with expertise in cardiac surgery may be faster than robotic novices with limited cardiac surgery experience, which may suggest that robotic skills training should only be commenced after the surgeons master the non-robotic techniques. However, if this is not the case, robotic skills training programs should be implemented early in cardiac surgeons' careers to allow them to develop expert-level skills as early in their careers as possible.

The current study will be the first to examine validity evidence for the wet lab robotic cardiac surgery model with the largest number of participants to-date and will be the first to analyze learning curves in wet lab simulation settings for subjects with different surgical background. Results of the study could help in establishing standardized training pathways in robotic cardiac surgery as recommended at the ORSI Consensus Meeting on European Robotic Training (OCERT) and facilitate faster spread of robotic cardiac surgery. Most importantly, establishing valid assessment methods will allow us to ensure that robotic surgeons are trained

until proficiency in the wet lab before operating being allowed to progress on real patients. This will ensure that all patients are certain to receive expert-level care regardless of where and by whom, they are treated.

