## **Objectives**

*Primary:*

- to investigate validity evidence for simulation-based assessment using the wet lab robotic cardiac surgery model.

*Secondary:*

- to analyze performance curves in the wet lab for a robotic cardiac surgery model.
- to assess rate of skills acquisition of cardiac robotic skills in cardiac surgery trainees versus non-cardiac surgery trainees.

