#### *Exclusion criteria*

- Novices with > 5 hours experience of any robotic system.

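### Training stage is uncontrolled in the 8 v 8 cardiac v non-cardiac comparison, and that specialty contrast cannot by itself support a train-early or train-late conclusion

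*Combined protocol and SAP*

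**What the plan says.** All references are to the combined protocol and SAP.

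- **Inclusion criteria.** The two novice groups are "Cardiac surgery novices: on-going or completed cardio-thoracic residency" and "Non-cardiac surgery novices: on-going or completed surgical specialty residency (gynecology, urology, general surgery, ENT surgery" (the specialty list ends there). Neither sets a training year or an operative volume.
- **Exclusion criteria.** The only limit on novice experience is robotic: "Novices with > 5 hours experience of any robotic system".
- **Objectives, secondary.** The contrast is "to assess rate of skills acquisition of cardiac robotic skills in cardiac surgery trainees versus non-cardiac surgery trainees".
- **Study rationale.** The motivating hypothesis is that "robotic novices with expertise in cardiac surgery may be faster than robotic novices with limited cardiac surgery experience". If so, this may suggest that "robotic skills training should only be commenced after the surgeons master the non-robotic techniques". If not, "robotic skills training programs should be implemented early in" cardiac surgeons' careers.
- **Secondary outcome measures.** The relevant outcome is training time to the mastery level, in total and per task.
- **Statistical plan and data analysis.** Eight cardiac and eight non-cardiac novices are planned. Continuous variables are compared by Mann-Whitney U at a two-sided 0.05 level. No section matches, stratifies, records or adjusts for novice training stage.

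**The concern.** Two separate problems follow.

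**Uncontrolled seniority.** A resident near the start of training and a fully qualified specialist can sit in the same group, and the mix may differ between groups. The rationale itself treats prior non-robotic surgical experience as something that may change the rate of learning. If one specialty supplies mostly completed specialists and the other mostly residents, that difference enters the cardiac v non-cardiac result and can create a difference or hide one.

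**Question and contrast do not match.** The rationale draws a conclusion about career stage within cardiac surgery: start robotic training early, or wait. The planned contrast is between specialties. A cardio-thoracic resident at any stage counts towards the cardiac arm, and a completed urologist or gynecologist counts towards the comparator. Junior and senior cardiac novices are pooled, so no listed analysis shows whether a junior cardiac surgeon should wait. This holds even if seniority is perfectly balanced.

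At stake is a recommendation on when to start robotic training, from a study whose stated aim includes helping to establish standardized training pathways.

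**Working it through.** The documents give no effect size, SD or power for this comparison, so there is no stated figure to reproduce. What follows illustrates the size under labelled assumptions.

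**From the documents:** 8 v 8, unadjusted Mann-Whitney U, two-sided 0.05.

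**Assumed:** normal scores with SD 1 within training stage; completed specialists differ from residents by g = 1 or 1.5 SD; exact test; 4,000 to 8,000 simulated trials per setting. Rates moved by about one percentage point between runs.

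**1. Bias for a given split.** With k1 and k2 completed specialists in the two groups,

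bias = (k1 − k2) / 8 × g.

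- 6 v 2: 4/8 × 1 = 0.50 SD; 4/8 × 1.5 = 0.75 SD.
- 7 v 1: 6/8 × 1 = 0.75 SD; 6/8 × 1.5 = 1.125 SD.

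**2. False positives with no specialty effect, split held fixed.**

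| Completed, group 1 v group 2 | g = 1 SD | g = 1.5 SD |
|---|---|---|
| 4 v 4 | 2.6% | 1.7% |
| 5 v 3 | about 4% | 4–5% |
| 6 v 3 | 7% | 9% |
| 6 v 2 | 11–12% | 16% |
| 7 v 1 | 25% | 44–45% |

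**3. Masking.** With a true cardiac advantage of 1.5 SD and g = 1 SD, power is about 69% at 4 v 4. It falls to about 37% if 2 cardiac and 6 non-cardiac novices are completed specialists.

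**4. Does chance imbalance alone cause harm?** Suppose each novice, in either group, is equally likely to be on-going or completed. The difference in completed numbers between two groups of 8 then has the distribution of Bin(16, 0.5) − 8:

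- gap of 3 or more: 2 × 6,885 / 65,536 = 21%
- gap of 4 or more: 2 × 2,517 / 65,536 = 7.7%
- gap of 6 or more: 2 × 137 / 65,536 = 0.4%

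Under this model the groups are exchangeable when there is no specialty effect, so the test keeps its level. Simulated false positives were 5.2%, 4.9% and 4.4% at g = 1, 1.5 and 2 SD. Chance gaps are common, but the 5% already allows for them.

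**5. Can the specialty result carry the early/late inference?**

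- The inference needs on-going v completed within cardiac surgery. The plan supplies cardiac v non-cardiac, pooled over stage.
- A null result would be weak support for early training in any case: with no stage effect, the 8 v 8 test has about 45% power at a 1 SD difference and about 82% at 1.6 SD.
- A direct 4 v 4 contrast within the cardiac group is weaker still. The smallest exact two-sided p is 2/C(8,4) = 2/70 = 0.029 and the next is 4/70 = 0.057, so only complete separation is significant. Power is about 14%, 29% and 49% at 1, 1.5 and 2 SD.

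**The case against.** **Seniority is not confounded by design.** Both groups have the same eligible range, and nothing in the documents shows that recruitment will differ by specialty. A reader might infer from the 21% chance of a gap of 3 or more that the false-positive rate is raised. It is not, as step 4 shows. This part of the objection stands: excess error needs recruitment that differs systematically by specialty, and the direction of any bias is unknown. The 6 v 2 and 7 v 1 rates are conditional on those splits and on assumed stage effects. At 5 v 3 there is no inflation.

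**The planned test matches the stated objective.** The objective is cardiac v non-cardiac, surgeons from other specialties are a reasonable proxy for limited cardiac experience, the rationale hedges its late-training inference, and no outcome or test is framed as early v late. This is fair, and the specialty comparison is legitimate in its own right. It does not rescue the inference in the rationale, which concerns when in a career to train and which the pooled contrast does not address.

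**Wording.** That a first-year resident could enter is inferred from on-going residency; the text does not say so, though nothing excludes it. The objective's word trainees may simply mean people undergoing this training, so little should rest on it.

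**The repair does not settle the early/late question.** This is correct. Four against four cannot do so, and the on-going/completed split still places a first-month and a final-year resident in one stratum. That is why training year and operative volume should be recorded as well, and the conclusion limited.

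**Conclusion.** The point holds in two parts. First, training stage is neither balanced nor adjusted for in a non-randomised 8 v 8 comparison, which leaves it open to seniority bias if recruitment differs by specialty. Under assumed stage effects of 1 to 1.5 SD and no specialty effect, false positives would be about 11–16% at a 6 v 2 split and 25–45% at 7 v 1. Second, whatever the balance, the pooled specialty contrast cannot support the train-early or train-late inference in the Study rationale. This second part rests on the text alone.

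A reader might go further and conclude that the comparison is biased as designed, or that the study's main result is at risk. The documents support neither. Eligibility is the same in both groups, and the primary objective, with its baseline comparison of experts and novices, is unaffected. This is a cheap improvement to a secondary objective.

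**What to change.** - **Inclusion criteria:** keep 8 and 8, with a target of 4 on-going and 4 completed residencies in each novice group. Record training year and operative volume for every novice and report them by group.
- **Statistical plan and data analysis:** compare cardiac with non-cardiac novices by a rank test stratified by on-going/completed. Report on-going v completed among cardiac novices (4 v 4) as descriptive only.
- **Study rationale or statistical plan:** state that the specialty contrast alone does not support a recommendation on early or late robotic training.

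**Cost:** no extra participants; somewhat slower recruitment to fill each cell; one stratum and one sentence. Stratifying brings no gain in power (about 65%, against 69% for a balanced unstratified test, at a 1.5 SD specialty effect and a 1 SD stage effect). The benefit comes from the quota, which removes the between-group difference in the share completed. The stratified test keeps the comparison within stage if the quota is narrowly missed. The mix should be set at recruitment, because with 8 per group a lopsided split cannot be reliably repaired in the analysis.
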